## 14.2 Visual Acuity

Visual acuity is discussed in section 13.5.2 for the efficacy analysis. For safety, continuous descriptive statistics will be used to summarize visual acuity by eye and treatment group. Change from baseline will also be summarized. The Safety table will be produced with an additional categorical summary of subjects with logMAR change from baseline  $\geq 0.20$  logMAR and both eyes, Right Eye (OD) and Left Eye (OS) will be the unit of analysis.

## 14.3 Slit-Lamp Biomicroscopy Examination

Slit lamp biomicroscopy examination is discussed in section 13.5.3 for the efficacy analysis. For safety, descriptive statistics will be used to summarize slit-lamp biomicroscopy by eye and treatment group in the Safety population. Right Eye (OD) and Left Eye (OS) will be the unit of analysis.

#### 14.4 Undilated Fundoscopy Examination

Undilated Fundoscopy examinations will be performed at Visits 1 and 5. The exam will assess the following components, by eye:

- Vitreous Humour
- Optic nerve
- Macula
- Cup to disc ratio (vertical)

The Investigator will classify the results as Normal, Abnormal CS, or Abnormal NCS.

The results will be summarized using counts and percentages for each treatment group at each visit for each eye. Percentages will be based on the number of subjects in each treatment group with responses. Shift tables will also be provided comparing the follow-up visit to baseline.

All undilated fundoscopy will be presented in a subject listing.

#### 14.5 Intraocular Pressure (IOP)

Intraocular Pressure (IOP) will be assessed by applanation tonometry in each eye at Visits 1, 5, and 7. Results will be taken from a single measurement and will be recorded in mmHg.

Continuous descriptive statistics will be used to summarize the IOP by visit, eye and treatment group. Change from baseline will also be summarized.

During the Study Treatment Phase, the changes from baseline will be relative to the Study Treatment Phase baseline. During the Placebo Cross-over Phase, the changes from baseline will be relative to the Placebo Cross-over Phase baseline.

All IOP results will be presented in a subject listing.

#### 14.6 Clinical Laboratory Data

Blood samples for clinical laboratory parameters will be collected at Visits 1, 4, 5, and 7.

Clinical laboratory data includes Complete Blood Count (CBC) with differential, metabolic panel, standard GvHD panel, and an endocrine panel (at Visits 1, 5, and 7 only).

The quantitative variables will be summarized by treatment group with continuous descriptive statistics. The qualitative variables (counts and percentages) will be summarized by treatment group at each visit and time point (where appropriate). Change from baseline will also be summarized by treatment group.

The specific parameters and normal ranges are shown below.

All laboratory results will be presented in a subject listing.

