### 2.4 Other Variables

Other variables include laboratory tests for:

- Complete Blood Count (CBC) with differential
- Metabolic panel
- Other Standard GvHD
- Endocrine panel for the assessment of hypothalamic-pituitary-adrenal axis (HPA) function and for Progesterone to detect whether applied drug product is detected in the blood

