## **8.4 Data Analysis Conventions**

The Primary analysis will be performed by Statistics & Data Corporation (SDC) after the Study Treatment Phase is completed and the database has been locked and released for unmasking. An additional analysis will be completed once the Cross-over Phase is completed and the database for that portion is locked. Statistical programming and analyses will be performed using SAS® version 9.4 or higher. Output will be provided in rich text format (RTF) for tables, Excel format for tables and listings, and portable document format (PDF) for figures using landscape orientation for any PDF or RTF. All study data will be listed by subject, treatment, and visit (as applicable) based on all randomized subjects unless otherwise specified.

Summaries for continuous and ordinal variables will include the number of observations (n), arithmetic mean, standard deviation (SD), median, minimum, and maximum. Minima and maxima will be reported with the same precision as the raw values; means and medians will be presented to one additional decimal place than reported in the raw values. Standard deviations will be presented to two additional decimal places than reported in the raw values. Summaries for discrete variables will include counts and percentages. All percentages will be rounded to one decimal place (ie, XX.X%). Differences between active treatment group and placebo will be calculated as active minus placebo and change from baseline will be calculated as follow-up visit minus baseline.

All statistical tests will be two-sided with a significance level of 0.05 ( $\alpha = 0.05$ ) unless otherwise specified. Confidence intervals (CI) for differences between treatment groups will be two-sided at 95% confidence intervals. All p-values will be rounded to 4 decimal places; p-values less than 0.0001 will be presented as "<0.0001"; p-values greater than 0.9999 will be presented as ">0.9999."

Unless otherwise specified, summaries will be presented by treatment group and, where appropriate, visit. Listings will be sorted by treatment group, subject number, visit/time point, and parameter as applicable.

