Table 14.3.4.1	Laboratory Results - Complete Blood Count Shifts from Baseline	Safety Population
Table 14.3.4.2	Laboratory Results - Metabolic Panel Shifts from Baseline	Safety Population
Table 14.3.4.3	Laboratory Results - Standard GvHD Panel	Safety Population
Table 14.3.4.4	Laboratory Results - Endocrine Panel	Safety Population
Table 14.3.5.1	Visual Acuity in LogMAR Units	Safety Population
Table 14.3.5.2	Slit Lamp Biomicroscopy Without Staining	Safety Population
Table 14.3.5.3	Slit Lamp Biomicroscopy Without Staining – Shift Table	Safety Population
Table 14.3.5.4	Undilated Fundoscopy Findings	Safety Population
Table 14.3.5.4	Undilated Fundoscopy Findings – Shift Table	Safety Population
Listings	Title	Population
Listing 16.1.7	Randomization Schedule	All Subjects
Listing 16.2.1	Subject Disposition and Informed Consent	All Subjects
Listing 16.2.2	Protocol Deviations	All Subjects

Listing 16.2.3.1	Demographics	All Subjects
Listing 16.2.3.2	Ocular Medical History	All Subjects
Listing 16.2.3.3	Non-Ocular Medical History	All Subjects
Listing 16.2.3.4	Prior and Concomitant Medication or Device History	All Subjects
Listing 16.2.4.1	Study Medication Accountability Log	All Subjects
Listing 16.2.4.2	Ocular Medication Log & Eye Drop Usage	All Subjects
Listing 16.2.5.1	Glia Ocular Surface Disease Symptoms Questionnaire, In Clinic	All Subjects
Listing 16.2.5.2	Glia Ocular Surface Disease Symptoms Questionnaire, Daily Diary	All Subjects
Listing 16.2.5.3	Modified Symptom Assessment iN Dry Eye (SANDE) Questionnaire	All Subjects
Listing 16.2.5.4	National Institutes of Health (NIH) Ocular Graft-versus-Host Disease (GvHD) Score	All Subjects
Listing 16.2.5.5	TearScan Examination	All Subjects
Listing 16.2.5.6	Corneal and Conjunctival Fluorescein Staining Examination All Subject	All Subjects
Listing 16.2.5.7	Facial Presentation and Blinks per Minute by Video Camera All Subject	All Subjects
Listing 16.2.6	All Adverse Events	All Subjects
Listing 16.2.7.1	Visual Acuity	All Subjects
Listing 16.2.7.2	Slit Lamp Biomicroscopy (SLB) Without Staining All Subject	All Subjects
Listing 16.2.7.3	Intraocular Pressure (IOP)	All Subjects
Listing 16.2.7.4	Undilated Fundoscopy Examination All Subject	All Subjects
Listing 16.2.8.1	Pregnancy Test Results	All Subjects
Listing 16.2.8.2	Laboratory Results - Complete Blood Count	All Subjects
Listing 16.2.8.3	Laboratory Results - Metabolic Panel	All Subjects
Listing 16.2.8.4	Laboratory Results - GvHD Panel	All Subjects

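### Endocrine panel: summaries by arm pool men and women with very different normal ranges, so a small progesterone rise can be hidden; add counts against each subject's own range (minor)

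*SAP*

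**What the plan says.** SAP 2.4 (Other Variables) gives the endocrine panel two purposes. One is the assessment of HPA function. The other concerns the drug itself: "and for Progesterone to detect whether applied drug product is detected in the blood".

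SAP 14.6 sets out the laboratory analysis. For measured values it says "The quantitative variables will be summarized by treatment group with continuous descriptive statistics", and then "Change from baseline will also be summarized by treatment group". SAP 8.4 defines the statistics as the number of observations, "arithmetic mean, standard deviation (SD), median, minimum, and maximum". It makes change an absolute difference: "change from baseline will be calculated as follow-up visit minus baseline". SAP 14.6 also promises counts and percentages for qualitative variables, but names none for hormones. All results go into a listing, and SAP 8.4 adds: "Listings will be sorted by treatment group, subject number, visit/time point, and parameter as applicable".

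SAP Table 6 prints hormone ranges that depend on sex, age, cycle phase or menopausal status. Its footnote speaks of the reference ranges that the final tables will use. It attaches no flag, rule or count to them.

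In SAP 19, the blood-count and metabolic tables are titled as shifts (for example "Laboratory Results - Metabolic Panel Shifts from Baseline"). The endocrine table, 14.3.4.4, is not.

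**The concern.** Whether applied drug shows up in blood is a yes-or-no question about each subject. The stated summary answers a different question, namely what the arm looks like on average and at its extremes. That would be adequate if everyone shared one range. They do not: the trial enrols adults of both sexes and allows women of childbearing potential who use contraception. A value that is ordinary for a cycling woman is far outside the range for a man.

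The protocol's safety reasoning relies on low absorption. It gives 0.7 mg progesterone per application, so 2 × 0.7 = 1.4 mg a day, and says that less than 5% crosses the outer skin layer. Serum progesterone is the direct check of that premise in these subjects. A rise, if there is one, could well be small (an inference, since the documents give no expected serum level). A small rise is the kind that pooled statistics can lose. The reader would then have to tally the listing by hand against each subject's own range.

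**Working it through.** The plan gives no figure to reproduce, so the check is an illustration built on the printed limits.

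**From the documents.** Arms of 22 and 11 (SAP 5). Progesterone in ng/mL (SAP Table 6): men below 0.20, post-menopausal women up to 0.20, follicular phase up to 0.89, luteal phase 1.8 to 24. Summary statistics as in SAP 8.4.

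**Assumed.** The active arm has one cycling woman, unaffected by the drug, at 0.5 at baseline and L at follow-up. The other 21 are men or post-menopausal women at 0.10. Of these, r rise to 0.60 (three times their limit, a gain of 0.50), and the rest do not change.

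**Step 1, spread of the limits.** 24 / 0.20 = 120.

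**Step 2, planned statistics.**
- Mean change = ((L − 0.5) + 0.5r) / 22
- Variance of change = ((L − 0.5)² + 0.25r − 22 × mean²) / 21
- Standard error = SD / √22

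L is set at the two luteal limits and at their midpoint, (1.8 + 24)/2 = 12.9.

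| L | r | Mean change | SD | SE | Median change | Maximum value |
|---|---|---|---|---|---|---|
| 12.9 | 0 | 12.4/22 = 0.564 | 2.644 | 0.564 | 0 | 12.9 |
| 12.9 | 4 | 14.4/22 = 0.655 | 2.631 | 0.561 | 0 | 12.9 |
| 24 | 0 | 23.5/22 = 1.068 | 5.010 | 1.068 | 0 | 24 |
| 24 | 4 | 25.5/22 = 1.159 | 4.994 | 1.065 | 0 | 24 |
| 1.8 | 0 | 1.3/22 = 0.059 | 0.277 | 0.059 | 0 | 1.8 |
| 1.8 | 4 | 3.3/22 = 0.150 | 0.323 | 0.069 | 0 | 1.8 |

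**Step 3, reading it.** Four absorbers always move the mean by 4 × 0.5/22 = 0.091. At L = 12.9 that is 0.091/0.561 = 0.16 standard errors, and the SD barely changes. At L = 24 it is 0.091/1.065 = 0.09. At L = 1.8 it is 0.091/0.069 = 1.3, and the SD also rises, from 0.277 to 0.323. So masking is near complete at mid or high luteal values and only partial at the low end. The maximum does not move in any row.

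**Step 4, when there is no masking.** If all 22 start at 0.10 and four rise, the mean change is 0.091, the maximum value 0.60 and the maximum change +0.50. The rise shows, although not how many subjects had it. If the woman is luteal at baseline and at 0.5 afterwards, the follow-up maximum is again 0.60 and the maximum change +0.50.

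**Step 5, an own-range count.** The masked case would read 4/21 active against 0/11 placebo, if all 11 can be classified and none rises. Fisher's exact p is 0.27, so the count describes and does not test. If all 22 active subjects could be classified and none crossed, the one-sided 95% upper bound on the rate would be 1 − 0.05^(1/22) = 12.7%.

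**The case against.** The best reply is that nothing is lost. The listing is sorted by arm and holds every value for 33 subjects. The Protocol (V, Study Procedures) has the transplant physicians review the results. The planned minimum and maximum may show an outlier. The Table 6 footnote implies that ranges will be used in the output, and the promised counts for qualitative variables could be read as range categories. SAP 14.6 does not mention the blood-count and metabolic shift tables either, yet both are titled in SAP 19. Nor does SAP 19 mirror the text fully: SAP 13.5.4 promises staining shift tables that it does not list.

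Much of this stands. Individual subjects are protected, and the table titles are only supporting evidence. But neither the footnote nor the qualitative-variable sentence defines a hormone category, and a listing leaves the count to the reader.

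Three stronger readings are tempting and are not supported.

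- A reader might infer that masking is likely. With 2:1 allocation, a single cycling woman among the 33 has a 22/33 = 67% chance of being in the active arm. That is not the chance of masking, which also needs a low baseline and a high follow-up value. The documents do not give the number of such women.
- A reader might extend the point to ACTH and the thyroid tests in Table 14.3.4.3. In SAP Table 5, ACTH and TSH have one range each, and T3 and T4 split only at age 20. The pooling argument gives no reason to change that table.
- A reader might argue from the width of the testosterone or DHEA-S ranges that large falls could be hidden. That needs a subject to cross the whole normal range between visits, and nothing in the documents suggests it.

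**Conclusion.** The point holds as a minor improvement in safety reporting. The SAP asks whether applied progesterone is found in blood, but for the endocrine hormones it states only arm-level descriptive statistics, change and a listing. One cycling woman in the active arm with a high follow-up value can hide a small rise in other subjects, wholly or partly, in the mean, SD and maximum. Without her, the planned maximum reveals it. The limits and the 22:11 split come from the documents. The hormone values, the number of absorbers and the presence of the woman are assumptions, and how probable the masked case is cannot be known. Efficacy conclusions are not affected, and SAP 2.4 places these tests outside its efficacy and safety variable lists.

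**What to change.** In Table 14.3.4.4, by arm and visit:

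- Report the number of men and post-menopausal women whose progesterone goes from at or below 0.20 ng/mL at baseline to above it, with the number classifiable as denominator. Show other women in a separate row.
- Add low/normal/high shifts from baseline for the other hormones with sex- or age-specific ranges: DHEA-S, FSH, LH, testosterone, and estradiol where a range exists. Use each subject's own Table 6 range.
- Leave a value unclassified where the range or cycle phase is unknown, for example male estradiol, which has no printed range.
- Include Visit 4 results where collected. SAP 14.6 limits the endocrine panel to Visits 1, 5 and 7, but SAP Table 2 and the Protocol also schedule it at Visit 4.

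The cost is a little programming in a format already planned for two other panels, with no new samples or visits. Menopausal status is not among the demographics in SAP 10. It must be taken from medical history and may be missing for some women. Counts will be small and descriptive only. A subject already above the limit at baseline cannot show a new crossing, and a rise within range is not counted. Crossing 0.20 ng/mL is therefore a practical marker and does not prove or rule out absorption.

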**Table 3. Complete Blood Count and Differential Parameters and Normal Ranges**

Complete Blood Count Panel Parameter	Normal Range*
WBC	3.81 - 8.94 K/uL
RBC	4.35 - 5.61 M/uL
HGB	12.5 - 16.3 g/dL
HCT	37.1 - 49.5 %
PLT	152 - 440 K/uL
MCV	79.0 - 97.0 fL
MCH	26.2 - 32.0 pg
MCHC	33.3 - 35.7 g/dL
RDW	12.1 - 16.0 %
MPV	7.0 - 10.8 fL
NRBC	0.00 /100 WBCs
ABSOLUTE NRBC	K/uL
NEUTS	46.5 - 82.4 %
EOSINOPHIL	0.1 - 6.0 %
BASOPHIL	0.1 - 1.1 %
LYMPHHS	8.5 - 32.7 %
MONOS	5.4 - 14.2 %
ABSOLUTE NEUTS	2.23 - 6.11 K/uL
ABSOLUTE EOS	0.00 - 0.52 K/uL
ABSOLUTE BASO	0.00 - 0.11 K/uL
ABSOLUTE LYMPHHS	0.21 - 2.74 K/uL
ABSOLUTE MONOS	0.2 - 0.87 K/uL

\*Reference ranges may change at the time of analysis. Any changes to the reference ranges used in the final tables will be approved by the client and will be documented in the clinical summary report.

**Table 4. Comprehensive Metabolic Panel Parameters and Normal Ranges**

Comprehensive Metabolic Panel Parameter	Normal Range*
SODIUM	135 - 145 mmol/L
POTASSIUM	3.5 - 5.0 mmol/L
CHLORIDE	98 - 108 mmol/L
CO2	23 - 32 mmol/L
BUN	9 - 25 mg/dL
CREATININE	0.7 - 1.3 mg/dL
GLUCOSE	70 - 100 mg/dL
ALBUMIN	3.7 - 5.4 g/dL
TOTAL PROTEIN	6.0 - 8.0 g/dL
CALCIUM	8.8 - 10.5 mg/dL
ALKALINE PHOSPHATASE	36 - 118 U/L
TOTAL BILIRUBIN	0.2 - 1.2 mg/dL
AST	9 - 30 U/L
ALT	7 - 52 U/L
GLOBULIN	2.3 - 4.2 g/dL
EGFR	>59 mL/min/1.73m 
ANION GAP	5 - 17 mmol/L

\*Reference ranges may change at the time of analysis. Any changes to the reference ranges used in the final tables will be approved by the client and will be documented in the clinical summary report.

**Table 5. Standard GvHD Panel Parameters and Normal Ranges**

Standard GvHD Panel Parameter	Normal Range*
TACROLIMUS	3.0 - 15.0 ng/mL
SIROLIMUS	3.0 – 12.0 ng/mL
VITAMIN D Total, 25-OH (D2 and D3) Sunquest Lab, OHDT	20-80 ng/mL
T4 (thyroxine), Total, Serum	11-19 years: 5.9-13.2 µg/dL Adult (> or =20 years): 4.5-11.7 µg/dL
T4 (thyroxine), Free, Serum	11-19 years: 1.0-1.6 ng/dL Adult (> or =20 years): 0.9-1.7 ng/dL
T3 (triiodothyronine), Total, Serum	11-19 years: 91-218 ng/dL Adult (> or =20 years): 80-200 ng/dL
ACTH (adrenocorticotropic hormone), Plasma	7.2-63 pg/mL (a.m. draws)
TSH (thyroid stimulating hormone), Serum	0.27 - 4.20 µIU/mL

\*Reference ranges may change at the time of analysis. Any changes to the reference ranges used in the final tables will be approved by the client and will be documented in the clinical summary report.

**Table 6. Endocrine Panel Parameters and Normal Ranges**

Endocrine Panel Parameter	Normal Range*
DHEA-S (dehydroepiandrosterone sulfate), Serum	18-30 years: 105-728 µg/dL 31-40 years: 57-522 µg/dL 41-50 years: 34-395 µg/dL 51-60 years: 20-299 µg/dL 61-70 years: 12-227 µg/dL > or =71 years: 6.6-162 µg/dL
ESTRADIOL, Serum	Follicular Phase 27-156 pg/mL Mid Cycle Peak 48-314 pg/mL Luteal Phase 33-298 pg/mL Postmenopausal <50 pg/mL
FSH (follicle stimulating hormone), Serum	Male 1.6-8.0 mIU/mL Female Follicular Phase 2.5-10.2 mIU/mL Mid-Cycle Peak 3.1-17.7 mIU/mL Luteal Phase 1.5- 9.1 mIU/mL Postmenopausal 23.0-116.3 mIU/mL
LH (luteinizing hormone), Serum	Male 18-59 Years 1.5-9.3 mIU/mL ≥60 Years 1.6-15.2 mIU/mL Female Follicular Phase 1.9-12.5 mIU/mL Mid-Cycle Peak 8.7-76.3 mIU/mL Luteal Phase 0.5-16.9 mIU/mL Postmenopausal 10.0-54.7 mIU/mL
PTH (Parathyroid Hormone), Serum	15-65 pg/mL

Endocrine Panel Parameter	Normal Range*
PROGESTERONE, Serum	
MALES > or =18 year: <0.20 ng/mL
 
FEMALES > or =18 years:
 
 
-Follicular phase: < or =0.89 ng/mL
 
-Ovulation: < or =12 ng/mL
 

	
 
-Luteal phase: 1.8-24 ng/mL
 
-Post-menopausal: < or =0.20 ng/mL
 
-Pregnancy
 
- 1st trimester: 11-44 ng/mL
 
- 2nd trimester: 25-83 ng/mL
 
- 3rd trimester: 58-214 ng/mL
 

TESTOSTERONE, Total and Free, Serum Mayo Clinic test code TGRP	
TESTOSTERONE, FREE
 
Males (adult):
 
20-<25 years: 5.25-20.7 ng/dL
 
25-<30 years: 5.05-19.8 ng/dL
 
30-<35 years: 4.85-19.0 ng/dL
 
35-<40 years: 4.65-18.1 ng/dL
 
40-<45 years: 4.46-17.1 ng/dL
 
45-<50 years: 4.26-16.4 ng/dL
 
50-<55 years: 4.06-15.6 ng/dL
 
55-<60 years: 3.87-14.7 ng/dL
 
60-<65 years: 3.67-13.9 ng/dL
 
65-<70 years: 3.47-13.0 ng/dL
 
70-<75 years: 3.28-12.2 ng/dL
 
75-<80 years: 3.08-11.3 ng/dL
 
80-<85 years: 2.88-10.5 ng/dL
 
85-<90 years: 2.69-9.61 ng/dL
 
90-<95 years: 2.49-8.76 ng/dL
 
95-100+ years: 2.29-7.91 ng/dL
 
Females (adult):
 
20-<25 years: 0.06-1.08 ng/dL
 
25-<30 years: 0.06-1.06 ng/dL
 
30-<35 years: 0.06-1.03 ng/dL
 
35-<40 years: 0.06-1.00 ng/dL
 
40-<45 years: 0.06-0.98 ng/dL
 
45-<50 years: 0.06-0.95 ng/dL
 
50-<55 years: 0.06-0.92 ng/dL
 
55-<60 years: 0.06-0.90 ng/dL
 
60-<65 years: 0.06-0.87 ng/dL
 
65-<70 years: 0.06-0.84 ng/dL
 
70-<75 years: 0.06-0.82 ng/dL
 
75-<80 years: 0.06-0.79 ng/dL
 
80-<85 years: 0.06-0.76 ng/dL
 
85-<90 years: 0.06-0.73 ng/dL
 
90-<95 years: 0.06-0.71 ng/dL
 
95-100+ years: 0.06-0.68 ng/dL
 
TESTOSTERONE, TOTAL
 
Males
 
17-18 years: 300-1,200 ng/dL
 
> or =19 years: 240-950 ng/dL
 
Females

Endocrine Panel Parameter	Normal Range*
	17-18 years: 20-75 ng/dL > or =19 years: 8-60 ng/dL

\*Reference ranges may change at the time of analysis. Any changes to the reference ranges used in the final tables will be approved by the client and will be documented in the clinical summary report.

## 15. Interim Analyses

No interim analyses are planned for this study.

## 16. Changes from Protocol-Stated Analyses

The protocol and SAP call for LOCF imputation and for sensitivity analyses in the Per Protocol population for the key efficacy endpoints. Given there is only 1 early discontinuation and no expected major protocol deviations, the LOCF imputation and Per Protocol population have been removed due to the expected similarity with the ITT Population using only observed data. The protocol calls for t-tests and ANCOVA analyses for ordinal data, It has been decided that the Wilcoxon Rank Sum Test will be sufficient and the t-test and ANCOVA will not be done.

All crossover data collected will be summarized with continuous descriptive statistics or with counts and percentages as appropriate.

Interblink interval may appear in the protocol however all instances of interblink interval have been changed to Facial Presentation and Blinks per Minute

Per the Sponsor an additional ANCOVA model including eye type has been added for the key efficacy variables.

Additional exploratory analyses may be requested after final analyses and may be detailed in the clinical study report.

## 17. References

None.

## 18. Revision History

Documentation of revision to the SAP will commence after approval of the final version 1.0.

## 19. Tables, Listings and Figures

Tables	Title	Population
Table 14.1.1	Subject Disposition	All Enrolled Subjects
Table 14.1.2	Demographic and Iris Color	ITT Population

Table 14.1.3.1	Ocular Medical History	ITT Population
Table 14.1.3.2	Non-Ocular Medical History	ITT Population
Table 14.1.4.1	Ocular Concomitant Medications Intent-to-Treat Population	ITT Population
Table 14.1.4.2	Non-Ocular Concomitant Medications Intent-to-Treat Population	ITT Population
Table 14.1.5	Study Drug Exposure in Days	Safety Population
Table 14.2.1.1	GLIA Ocular Surface Disease Symptoms Questionnaire, in Clinic by Eye	ITT Population
Table 14.2.1.2	GLIA Ocular Surface Disease Symptoms Questionnaire, in Clinic with Combined Eyes	ITT Population
Table 14.2.2.1	GLIA Ocular Surface Disease Symptoms Questionnaire, Daily Diary by Eye	ITT Population
Table 14.2.2.2	GLIA Ocular Surface Disease Symptoms Questionnaire, Daily Diary with Combined Eyes	ITT Population
Table 14.2.3.2	Modified SANDE - Symptom Assessment iN Dry Eye (SANDE) Questionnaire by Eye	ITT Population
Table 14.2.3.3	Modified SANDE - Symptom Assessment iN Dry Eye (SANDE) Questionnaire with Combined Eyes	ITT Population
Table 14.2.4.1.1	Slit Lamp Biomicroscopy Without Staining by Eye	ITT Population
Table 14.2.4.1.2	Slit Lamp Biomicroscopy Without Staining with Combined Eye	ITT Population
Table 14.2.4.1.3	Slit Lamp Biomicroscopy Without Staining – Shift Table	ITT Population
Table 14.2.4.2.1	Corneal and Conjunctival Fluorescein Staining Examination by Eye	ITT Population
Table 14.2.4.2.2	Corneal and Conjunctival Fluorescein Staining Examination with Combined Eye	ITT Population
Table 14.2.5	National Institute of Health (NIH) Eye Score	ITT Population
Table 14.2.6	Daily Use of Eye Drops	ITT Population
Table 14.2.7	TearScan Examination	ITT Population
Table 14.2.8	Visual Acuity in LogMAR Units	ITT Population
Table 14.2.9	Facial Presentation and Blinks per Minute	ITT Population
Table 14.3.1.1	Overall Summary of All Treatment-Emergent Adverse Events (TEAEs)	Safety Population
Table 14.3.1.2	Treatment-Emergent Adverse Events (TEAE) by System Organ Class (SOC) and Preferred Term (PT)	Safety Population
Table 14.3.1.3	Treatment-Emergent Adverse Events (TEAEs) by System Organ Class, Preferred Term, and Relationship to Study Drug	Safety Population
Table 14.3.1.4	Serious Treatment-Emergent Adverse Events (TEAEs) (Including Death) by System Organ Class (SOC) and Preferred Term (PT)	Safety Population
Table 14.3.4.1	Laboratory Results - Complete Blood Count Shifts from Baseline	Safety Population
Table 14.3.4.2	Laboratory Results - Metabolic Panel Shifts from Baseline	Safety Population
Table 14.3.4.3	Laboratory Results - Standard GvHD Panel	Safety Population
Table 14.3.4.4	Laboratory Results - Endocrine Panel	Safety Population
Table 14.3.5.1	Visual Acuity in LogMAR Units	Safety Population
Table 14.3.5.2	Slit Lamp Biomicroscopy Without Staining	Safety Population
Table 14.3.5.3	Slit Lamp Biomicroscopy Without Staining – Shift Table	Safety Population
Table 14.3.5.4	Undilated Fundoscopy Findings	Safety Population
Table 14.3.5.4	Undilated Fundoscopy Findings – Shift Table	Safety Population
Listings	Title	Population
Listing 16.1.7	Randomization Schedule	All Subjects
Listing 16.2.1	Subject Disposition and Informed Consent	All Subjects
Listing 16.2.2	Protocol Deviations	All Subjects

Listing 16.2.3.1	Demographics	All Subjects
Listing 16.2.3.2	Ocular Medical History	All Subjects
Listing 16.2.3.3	Non-Ocular Medical History	All Subjects
Listing 16.2.3.4	Prior and Concomitant Medication or Device History	All Subjects
Listing 16.2.4.1	Study Medication Accountability Log	All Subjects
Listing 16.2.4.2	Ocular Medication Log & Eye Drop Usage	All Subjects
Listing 16.2.5.1	Glia Ocular Surface Disease Symptoms Questionnaire, In Clinic	All Subjects
Listing 16.2.5.2	Glia Ocular Surface Disease Symptoms Questionnaire, Daily Diary	All Subjects
Listing 16.2.5.3	Modified Symptom Assessment iN Dry Eye (SANDE) Questionnaire	All Subjects
Listing 16.2.5.4	National Institutes of Health (NIH) Ocular Graft-versus-Host Disease (GvHD) Score	All Subjects
Listing 16.2.5.5	TearScan Examination	All Subjects
Listing 16.2.5.6	Corneal and Conjunctival Fluorescein Staining Examination All Subject	All Subjects
Listing 16.2.5.7	Facial Presentation and Blinks per Minute by Video Camera All Subject	All Subjects
Listing 16.2.6	All Adverse Events	All Subjects
Listing 16.2.7.1	Visual Acuity	All Subjects
Listing 16.2.7.2	Slit Lamp Biomicroscopy (SLB) Without Staining All Subject	All Subjects
Listing 16.2.7.3	Intraocular Pressure (IOP)	All Subjects
Listing 16.2.7.4	Undilated Fundoscopy Examination All Subject	All Subjects
Listing 16.2.8.1	Pregnancy Test Results	All Subjects
Listing 16.2.8.2	Laboratory Results - Complete Blood Count	All Subjects
Listing 16.2.8.3	Laboratory Results - Metabolic Panel	All Subjects
Listing 16.2.8.4	Laboratory Results - GvHD Panel	All Subjects
Listing 16.2.8.5	Laboratory Results - Endocrine Panel	All Subjects
Figures	Title	Population
Figure 14.2.1.1	GLIA Ocular Surface Disease Symptoms Questionnaire, in Clinic in the Worse Eye by Symptom	ITT Population
Figure 14.2.1.2	GLIA Ocular Surface Disease Symptoms Questionnaire, Daily Diary in the Worse Eye by Symptom	ITT Population
Figure 14.2.2.1	Modified SANDE - Symptom Assessment iN Dry Eye (SANDE) Questionnaire in the Worse Eye by Symptom	ITT Population
